1.1 Primary Objectives

Adult patients: (Study objectives met for adult cohort with Amendment K 02/01/13)

- To determine the response rate (PR + CR) of AZD2171 in adult patients with ASPS.
- To compare gene expression profiles between pre-treatment and on-treatment biopsy specimens.

Pediatric patients:

- To determine if pediatric patients with ASPS will experience at least a minimal response rate when treated with AZD2171.

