2.5 Correlative Studies

Current knowledge of potential therapeutic targets and their expression pattern in ASPS is limited. Only a few studies of small sample size, using archival pre-treatment tissue, have demonstrated some potentially targetable angiogenic factors [4, 30] through identification of up-regulated angiogenesis genes such as *angiogenin*, *HIF1 α* , *TGF β 1*, *JAG1*, *midkine*, *c-MET*, and *VEGF*. Paired pre- and post-treatment tumor biopsies would be of significant benefit in the quest for new target identification. In addition, early data from Phase II studies with the VEGFR blocker AZD2171 in treating patients with ASPS, as well as our own data, merit further understanding of the mechanism of action of this therapeutic agent. A major limitation to the study of therapeutic targets in ASPS is the rarity of this tumor, making access to human specimens difficult. This study provides the rare opportunity to acquire tissue. Paired pre- and post-treatment tumor biopsies would be of significant benefit in providing insight into the mechanism of action of AZD2171 by allowing detection of gene alterations as a direct consequence of AZD2171 effect and by comparing findings between responders and non-responders.

Tumor biopsies are not mandatory for participation in this protocol. For those willing to undergo biopsies, pre-treatment biopsies will be collected at baseline, and to try to detect early drug effect, a second biopsy will be performed between D3 and D5 of treatment and subjected to gene expression profiling. The time point for the second biopsy has been selected to maximize the possibility that any transcriptional changes seen are due to a direct drug mechanism of action versus any inflammatory infiltrate- or other endpoint-related findings. A third optional biopsy after completion of 4 weeks of therapy (between C1D28 and C2D7) may be collected with the intention of providing further information about disease response to treatment. The timing of the biopsies may change depending on findings from gene analysis. However, the total number of biopsies per patient will not change.

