9.1 Tissue Sample Acquisition and Processing (Adult Patients Only)

With Amendment K (02/01/2013), the adult cohort closed to accrual. No biopsies will be performed on this study.

For tumor biopsy site other than lung, two to three cores will be obtained. Samples will be divided as follows. If two cores are obtained, one core will be preserved in RNAlater for gene expression profiling. The other core biopsy sample will be divided such that 1/3 of the biopsy is fixed in 10% buffered formalin and submitted to Surgical Pathology, CCR/NCI ([name]) for routine diagnostic review, and the other 2/3 is flash frozen, shipped to PADIS, and kept for future analysis. If only one core is obtained, it will be divided in two (such that one half will be preserved in RNAlater, the remainder will be divided to provide material for flash freezing and for fixation in formalin for diagnostic review). If a third core is obtained, it will be flash frozen, shipped to PADIS, and kept for future analysis. For lung as site of tumor biopsy, an FNA sample only will be acquired and preserved in RNAlater for gene expression profiling.

9.1.1 *Timing of Biopsies*

Biopsies will be performed at the following times:

- Before starting treatment on study (baseline)
- Cycle 1, between Day 3 and Day 5
- A third optional tumor biopsy may be performed after completion of cycle 1 (between Cycle 1, Day 28 and Cycle 2, Day 7).

The timing of the post-treatment biopsies may be adjusted depending on initial gene expression profile results, but the total number of biopsies per patient will not change

9.1.2 *Biopsy Procedure*

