9.1.4 Processing of Patient Tumor Samples For RNA Analysis

Biopsy Sample Collection and Storage

- Biopsy samples will be collected in 2.0 mL eppendorf tubes (RNase and DNase free, sterile) filled with RNAlater RNA Stabilization Reagent (# 76106 Qiagen) and sealed with parafilm. (N.B.: Before use, check for RNAlater precipitate in tubes: in the unlikely event it is present, heat tubes at 37°C and agitate until completely dissolved).
- Maintain tubes upright
- Samples collected in the RNAlater can be held/stored at 2°C to 4°C OR room temperature until being shipped (within 48h).
- Ship via courier to:

[name]
Functional Genomics Lab
DTP, National Cancer Institute at Frederick
[name]
[name]
[contact] or [name]
[contact]

- Confirm time of courier pick-up to: [contact]

Sample Analysis

- Samples will be disrupted by FastPrep in RNA lysis buffer provided from Qiagen (RNeasy mini kit, #74106), and RNA will be extracted according to manufacturer's procedure.

- 100 ng of high quality RNA (Agilent RIN > 7) will be utilized for transcription profiling on Affymetrix U133 plus2 arrays, according to their protocols. The *.cel files will be analyzed by Partek and Gene Sifter, for evaluation of individual drug-modulated genes and impact on pathways.

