Biopsies will be obtained from as many patients as possible in the replicate cohort. The specimens will be subjected to gene expression profiling, with the analyses conducted under the direction of [name], Chief, Biometric Research Branch, DCTD. VEGFR pathway analysis will also be undertaken. If there are up to 3 independent outcome measures evaluated, and if 15 patients are able to provide biopsy specimens pre-treatment as well as at one or two times following treatment, then there would be 85% power for each difference from baseline equal to 1.0 SD of the difference (effect size =1) to be detected, using a 0.017 alpha level paired t-test for each evaluation. The 0.017 level for each of three comparisons will permit the overall family of tests to be performed at the 0.05 level, using an assumption of a very conservative Bonferroni adjustment for multiple comparisons. If there are up to 6 comparisons, there would be 76% power for each comparison, as a minimum. In practice, comparisons may be made using a Hochberg adjustment, which is not as overly conservative as the Bonferroni adjustment. Also, a Wilcoxon signed rank test may be used instead of a

paired t-test if the differences from pre-treatment are not normally distributed ($p < 0.05$ by a Shapiro-Wilks test).

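### Does the 0.05 family-wise level with 85% or 76% power in Section 13 fail because the array analysis looks at individual genes?

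*Combined protocol and SAP*

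**What the plan says.** Section 1.1 lists two primary objectives for adults. One is response rate; the other reads "To compare gene expression profiles between pre-treatment and on-treatment biopsy specimens". Section 2.5 explains the purpose of paired biopsies, in part: "by allowing detection of gene alterations as a direct consequence of AZD2171 effect". Section 9.1.4 names the array platform and the software, and says that the files will be analysed "for evaluation of individual drug-modulated genes and impact on pathways".

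Section 13 places the profiling analyses under the head of a biometrics branch and adds that the VEGFR pathway will be analysed. It then gives a power statement with explicit conditions. The first limits the number of tests: "If there are up to 3 independent outcome measures evaluated". Assuming paired biopsies from 15 patients, with one or two on-treatment samples each, every measure is tested by a paired t-test at 0.017 with 85% power for a difference of 1.0 SD. The level is justified thus: "The 0.017 level for each of three comparisons will permit the overall family of tests to be performed at the 0.05 level". A second condition follows: "If there are up to 6 comparisons, there would be 76% power for each comparison, as a minimum". A Hochberg adjustment may be used instead of Bonferroni, and a Wilcoxon signed rank test instead of the t-test if the differences are not normal.

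The three or six measures are not named. The supplied text mentions no false discovery rate, gene filter or gene-level threshold. Section 9.1.1 adds: "The timing of the post-treatment biopsies may be adjusted depending on initial gene expression profile results".

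**The concern.** The only error-control statement for this objective covers three to six tests, while the laboratory section describes an analysis of individual genes on an array. Bonferroni or Hochberg over six tests says nothing about thousands. If 0.017 were carried over to each gene, the family-wise level would be lost; if 0.05 were held across the array, the power would be lost.

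Because the measures are unnamed, three to six genes could also be picked after the arrays are read and reported as if the family had been fixed beforehand. The freedom to move biopsy times in response to early profiles adds to that worry. At stake is which gene-level claims a listed primary objective can support.

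**Working it through.** **Inputs from Section 13.** n = 15 pairs; difference = 1.0 SD of the paired difference; per-test level 0.017 for three comparisons. The per-test level for six is not stated; 0.05/6 = 0.0083 is assumed. Sidedness is not stated.

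**Reproducing the plan's power.** Paired t-test, 14 degrees of freedom, noncentrality 1.0 × √15 = 3.873. Power is the probability that a noncentral t variable falls outside ± the two-sided critical value.

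| Case | Level | Plan | Two-sided exact | One-sided exact |
|---|---|---|---|---|
| 3 comparisons | 0.017 | 85% | 86.0% | 92.4% |
| 6 comparisons | 0.05/6 | 76% | 77.2% | 85.8% |

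The two-sided test matches both figures to within about one point, so that is the test the plan used.

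**Reproducing the family-wise level.** The Bonferroni bound is 3 × 0.017 = 0.051. For independent tests, 1 − (1 − 0.017)³ = 0.0501. The excess over 0.05 is only the rounding of 0.05/3 = 0.0167 to 0.017.

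**What would happen if the same rules were carried to genes.** The documents do not give the number of genes m, so a range is assumed, with the effect still at 1.0 SD and independent tests.

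| m | Power at 0.05/m | Expected false positives at 0.017 each, all null (0.017 × m) |
|---|---|---|
| 100 | 34% | 1.7 |
| 1,000 | 11% | 17 |
| 10,000 | 2.7% | 170 |

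At m = 100 the chance of at least one false positive at 0.017 each is 1 − 0.983¹⁰⁰ = 82%. Bonferroni power is 82.5% at four tests and 79.7% at five.

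**How much these depend on assumptions.** With an effect of 1.5 SD (also an assumption), Bonferroni power at 100 tests is 86% instead of 34%.

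The customary array method is the Benjamini-Hochberg procedure. It was simulated at 10% with 10,000 independent genes and n = 15. With an effect of 1.0 SD and 1%, 5%, 10% or 20% of genes truly changed, average power is about 28%, 65%, 78% and 87%, and the false discovery rate stays below 10%. With 1.5 SD and 1% changed, power is about 92%. So the loss of power belongs to family-wise control over the array, not to gene-level analysis as such.

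**Is that procedure in the plan?** Section 13's level and power follow the conditions on three measures or six comparisons. The profiling and the VEGFR pathway analysis stand in separate sentences of the same paragraph with no level attached. Section 9.1.4 gives platform, software and purpose, but no threshold. No section joins 0.017 or 0.05 to a single gene.

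**The case for a change.** The strongest case for a change is that the objective is listed as primary, Section 13 holds the only error rate offered for it, and the analysis in Section 9.1.4 is plainly larger than six tests. The documents do not call the gene-level work exploratory. Hochberg is optional and is offered only for these few comparisons. Stored samples may still be analysed, and the trial update in Section 2.4 reports response but no expression results, so a reporting rule could still have effect. It would cost a few sentences.

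Two parts of this stand: the measures are unnamed, and the supplied text has no gene-level error rate. (Text between Sections 9.1.2 and 9.1.4 is not available, so the second point holds only for what was supplied.) The risk of choosing measures after the fact is real, and a report should say when any summary measure was fixed.

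The rest carries less weight. The power statement is explicitly conditional, so a reader who applies it to genes has to ignore its condition. Section 13 opens with response rate as the primary objective of the study; the biopsies are optional, are described under correlative studies, and enter no stopping or success rule. Naming measures in advance is probably out of reach: adult accrual closed with Amendment K in February 2013, Section 9.1 says no more biopsies will be done, and this version is dated November 2021.

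**Conclusion.** The concern does not call for a change. The 0.05 level and the 85% and 76% power are correct, to within about one point and the rounding of 0.05/3, for the three or six comparisons to which they are tied. The large figures for 100 to 10,000 genes illustrate a procedure that the plan does not state, and they rest on assumed gene counts, effect size and independence.

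What remains is a gap that analysts fill sensibly: a biometrics group directing array work can be expected to apply a standard false discovery rate method, state the rate and present single-gene findings as exploratory. Writing this into Section 13 now would fill a silence rather than replace a wrong method. It would alter no stated number, no accrual and no response-rate conclusion. This rests on reading Section 13's conditions as limits on its claim, and on the expression results being reported with the error rate actually used.

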Appendix A: Performance Status Criteria

PERFORMANCE STATUS CRITERIA Karnofsky and Lansky performance scores are intended to be multiples of 10.					
ECOG (Zubrod)		Karnofsky		Lansky	
Score	Description	Score	Description	Score	Description
0	Fully active, able to carry on all pre-disease performance without restriction.	100%	Normal, no complaints, no evidence of disease.	100%	Fully active, normal.
		90%	Able to carry on normal activity; minor signs of symptoms of disease.	90%	Minor restrictions in physically strenuous activity.
1	Restricted in physically strenuous activity but ambulatory, able to carry out light or sedentary work, e.g., light housework, office work.	80%	Able to carry on normal activity with effort; some signs or symptoms of disease.	80%	Active, but tires more quickly.
		70%	Cares for self, unable to carry on normal activity or do active work.	70%	Both greater restriction of, and less time spent in, play activities.
2	Ambulatory and capable of all self-care but unable to carry out any work activities. Up and about more than 50% of waking hours.	60%	Requires occasional assistance but is able to care for most of own needs.	60%	Up and around, but minimal active play; keeps busy with quieter activities.
		50%	Requires considerable assistance and frequent medical care.	50%	Gets dressed, but lies around much of the day; no active play; able to participate in quiet play and activities.
3	Capable of only limited self-care, confined to bed or chair more than 50% of waking hours	40%	Disabled; requires special care and assistance.	40%	Mostly in bed; participates in quiet activities.
		30%	Severely disabled; hospitalization indicated, although death not imminent.	30%	In bed; needs assistance even for quiet play.
4	Completely disabled. Cannot carry on any self-care. Totally confined to a bed or chair	20%	Very ill; hospitalization necessary; active supportive treatment required.	20%	Often sleeping; play entirely limited to very passive activities.
		10%	Moribund, fatal process progressing rapidly	10%	No play; does not get out of bed
5	Dead	0%	Patient expired	0%	Unresponsive; Dead

Appendix B: Enzyme-Inducing Anticonvulsant Drugs

For drugs not listed, please contact the Study Chair

Anticonvulsants with little or no enzyme induction	
Generic Name	Trade Name
Ethosuximide	Zarontin
Gabapentin	Neurontin
Lamotrigine	Lamictal
Levetiracetam	Keppra
Tigabine	Gabitril
Topiramate	Topamax
Valproic Acid	Depakote, Depakene
Zonisamide	Zonegran

Enzyme inducing anticonvulsant drugs (EIACD)	
Generic Name	Trade Name
Carbamazepine	Tegretol
Felbamate	Felbatol
Phenobarbital	Phenobarbital
Phenytoin	Dilantin
Primidone	Mysoline
Oxcarbazepine	Trileptal

Appendix C: Study Diary
Page 1

Today's date _____

Patient Name _____ Patient Study ID _____
(initials acceptable)

INSTRUCTIONS TO THE PATIENT:

1. Complete one form for each cycle.
2. You will take ____ pills (15mg) and ____ pills (20 mg) each day. Please take the pill(s) on an empty stomach either 1 hour before or 2 hours after meals.
3. Record the date, the number of pills you took, and when you took them.
4. If you have any comments or notice any side effects, please record them in the Comments column.
5. Please bring your pill bottle and this form to your physician when you go for your next appointment.

Date	Day	# pills and when taken	Blood Pressure		Symptoms
			morning	evening	
	1				
	2				
	3				
	4				
	5				
	6				
	7				
	8				
	9				
	10				
	11				
	12				
	13				
	14				

Patient's Signature: _____ Date: _____

Physician's Office will complete this section:

1. Date patient started protocol treatment _____ Date patient was removed from study _____
2. Patient's planned daily dose _____ Total number of pills taken this cycle _____

Physician/Nurse/Data Manager's Signature _____

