4.1 AZD2171 Administration

The adult cohort met study objectives and was closed to accrual with Amendment K, 02/01/13.

Adult patients will receive 30 mg AZD 2171 tablets orally once a day in a 28-day cycle. AZD2171 will be available as 15 and 20 mg tablets. The dose of 30 mg daily has been shown to be safe in multiple Phase I and II trials of AZD2171 as a single agent. In the early phase trial that showed activity of AZD2171 in patients with metastatic ASPS, the initial dose of AZD2171 was 45 mg po each day. However, most patients required a dose reduction to 30 mg po each day due to associated toxicities. Dose modifications are outlined in Section 5.

Pediatric patients will receive 12 mg/m²/dose (equivalent to 20 mg per dose based on a BSA of 1.8 m²) according to the Pediatric Dosing Nomogram (Appendix H). Dose adjustments may be made based on changes in height and weight in pediatric patients at the time of restaging evaluations. If the pediatric patient is unable to maintain the study diary independently, the following instructions will also be presented to the parent(s).

No investigational or commercial agents or therapies other than those described below may be administered with the intent to treat the patient's malignancy. Patients will take AZD2171 on an empty stomach (either 1 hour before or 2 hours after meals). The drug will be administered once daily at approximately the same time each day. Tablets must be swallowed whole and not crushed. A new cycle may begin 1 day earlier or 1 day later than it would otherwise be scheduled based on the 28-day cycle, to allow for flexibility for days the clinic is closed and other unexpected events.

Note: For patient convenience, 2 cycles' worth of drug may be dispensed at a time to patients who have been on study for over a year and are tolerating treatment well. For patients who have been on study for over 18 cycles, 3 cycles' worth of drug may be dispensed; for patients who have been on study for over 36 cycles, 4 cycles' worth of drug may be dispensed; for patients who have been on study for over 60 cycles, 6 cycles' worth of drug may be dispensed.

Patients will be provided with a Study Diary (Appendix C), instructed in its use, and asked to bring it with them to each appointment. A new copy of the Study Diary will be given to patients whose dose is reduced due to adverse events. After cycle 2, a cycle will be considered completed if 90% of the prescribed doses are administered.

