5.1 Dose Modifications

Dose will be modified for grade 3 or greater non-hematologic toxicity (except electrolyte abnormalities unless these are not correctable within 48 hours) and/or grade 4 hematologic (except lymphopenia, anemia) toxicity. A maximum of 2 dose reductions will be allowed before the patient is taken off treatment. Patients who require a dose-reduction will not have the dose re-escalated. No more than 2 dose reductions will be allowed.

If administration of AZD2171 is interrupted for any reason, counting of the cycle days continues (i.e., if a patient stops drug on Day 15 and resumes 2 days later, they will be considered on Day 17).

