5.1.2 Dose Modifications in Children (<16 years of age)

All pediatric patients will be started on the initial dose of 12 mg/m²/day (Appendix H) orally once per day for 28 days, in 28-day cycles. Dose adjustments based on changes in height and weight may be made every two cycles at the time of restaging evaluations when warranted (restaging CT scans will be performed every 2 cycles during the first 18 cycles; after 18 cycles, restaging CT scans will be performed every 3 cycles; after 36 cycles, restaging CT scans will be performed every 4 cycles; after 60 cycles, restaging CT scans will be performed every 6 cycles).

Dose Modification table for children:

INITIAL DOSE (mg/dose/day)	Reduced dose (mg/dose/day)	% Dose decrease from previous dose
30	20 mg/day	33

20	15 mg/day	25
15	15 mg/day daily for 5 days followed by 2 days rest *	29

*Patients who are receiving antihypertensive medication and require a dose reduction should take antihypertensive medication only on the days of cediranib administration.

Antihypertensive medication should be held during the 2 rest days.

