9.4.2 Follow-up Evaluation

- Plain radiographs of tibial growth plates will be performed if clinically indicated.
- Unilateral knee MRI: Growth plate MRIs will be repeated in subjects with open growth plates after cycles 2, 4, 8 and 12 (then every 4th cycle).

10 Study Calendar

Screening evaluations are to be conducted within 72 hours prior to administration of protocol therapy unless otherwise indicated. Diagnostic imaging must be done within 30 days prior to the enrollment on study. The research team may perform additional safety/monitoring tests as clinically indicated.

		Cycle 1				Cycles 2 and 3				Cycle 4 and subsequent cycles				
	Pre-Study	Wk 1	Wk 2	Wk 3	Wk 4	Wk 1	Wk 2	Wk 3	Wk 4	Wk 1	Wk 2	Wk 3	Wk 4	Off Study ^d
AZD2171 ^a		X	X	X	X	X	X	X	X	X	X	X	X	
Informed consent	X													
Demographics	X													
Medical history	X													
Concurrent meds	X	X-----								X				
Physical exam/vital signs/weight/ performance status ^{b,m}	X	X		X		X				X				X
EKG ^c	X													
Height ^l	X					X ^m								
Serum chemistry ^{d, m}	X	X	X	X	X	X		X		X				X
CBC w/diff, plts ^{e, m}	X	X	X	X	X	X		X		X				X
B-HCG ^f	X ^f													
Tumor measurements ^g	X	Tumor measurements are repeated as indicated below.												X
Urine dipstick or urinalysis for protein ^h	X	X	X	X	X	X		X		X				X
Echo/MUGA ⁱ	X													
Adverse event evaluation		X-----								X				X
TSH and T4	X					X				X				X
Plain radiograph of tibial growth plate ^j	X									X				
Unilateral knee MRI ^k	X ^l									X ^l				

- a: AZD2171: Dose as assigned administered orally, each day for 28 days (1 Cycle). Patients should keep a pill diary ([Appendix C](#)).
- b: BP monitoring should be performed by a health care provider every 2 weeks during cycles 1 and 2 and then at the start of each subsequent cycle, or more frequently if clinically indicated.
- c: At baseline and as clinically indicated.
- d: Albumin, alkaline phosphatase, total bilirubin, bicarbonate, BUN, calcium, chloride, creatinine, glucose, LDH, phosphorus, potassium, total protein, SGOT[AST], SGPT[ALT], sodium.
- e: CBC (WBC, Hgb, Hct, platelets, ANC, % neutrophils, bands, lymphocytes).
- f: Urine pregnancy test (women of childbearing potential).
- g: CT scan will be done at baseline and repeat imaging scans will be performed every 2 cycles during the first 18 cycles; after 18, 36, and 60 cycles, patients will have repeat imaging performed every 3,4,

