Appendix C: Study Diary
Page 2

Today's date _____

Patient Name _____ Patient Study ID _____
(initials acceptable)

INSTRUCTIONS TO THE PATIENT:

1. Complete one form for each cycle.
2. You will take ____ pills (15 mg) and ____ pills (20 mg) each day. Please take the pill(s) on an empty stomach either 1 hour before or 2 hours after meals.
3. Record the date, the number of pills you took, and when you took them.
4. If you have any comments or notice any side effects, please record them in the Comments column.
5. Please bring your pill bottle and this form to your physician when you go for your next appointment.

Date	Day	# pills and when taken	Blood Pressure		Symptoms
			morning	evening	
	15				
	16				
	17				
	18				
	19				
	20				
	21				
	22				
	23				
	24				
	25				
	26				
	27				
	28				

Patient's Signature: _____ Date: _____

Physician's Office will complete this section:

1. Date patient started protocol treatment _____ Date patient was removed from study _____
2. Patient's planned daily dose _____ Total number of pills taken this cycle _____

Physician/Nurse/Data Manager's Signature _____

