Appendix H: Pediatric Dosing Nomogram for AZD2171

Dose Level	Dose (mg/m ² /dose)			
1	12	BSA*	1.04-1.45	1.46-2.08
	Dose [†]	15		20
				30

* BSA, body surface area in m².

† Actual dose in mg (tablets sizes 15 and 20 mg) administered once daily.

Note: Dose reductions for patients experiencing dose-limiting toxicities are outlined in Section 5.1.2.

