 - If the BP returns to \leq ULN within 14 days, restart AZD2171 at a reduced dose (Section 5.1.2).
 - If the BP remains $>$ ULN for more than 14 days, patient is Off Protocol Therapy.
 - If the BP increases to $>$ 25 mm Hg above the ULN despite anti-hypertensive therapy, hold AZD2171, but continue the anti-hypertensive agent(s). Monitor the BP as clinically indicated and follow Arm 4 of the algorithm from the point that AZD2171 is held.
 - If the BP is \leq ULN within 14 days, AZD2171 may be restarted at a reduced dose (Section 5.1.2).
 - If the BP is $>$ ULN for $>$ 14 days, the patient is Off Protocol Therapy (Section 5.4).

Arm 4 of algorithm:

- If BP is $>$ 25 mm Hg above the 95% for age, height, and gender, hold AZD2171, monitor BP and administer anti-hypertensive therapy as clinically indicated.
 - If the BP returns to \leq ULN within 14 days, AZD2171 may be restarted at a reduced dose (Section 5.1.2).
 - If the BP is $>$ ULN for $>$ 14 days, the patient is Off Protocol Therapy (Section 5.4).

Arm 5 of algorithm:

- If the participant develops Grade 4 hypertension (CTCAE), discontinue AZD2171, monitor BP and administer anti-hypertensive therapy as clinically indicated. The patient is Off Protocol Therapy (Section 5.4).

Patients, who require a dose reduction of cediranib, which results in taking cediranib on days 1-5 followed by 2 days rest, should hold antihypertensive medication on the rest days when they are not taking cediranib.

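### The Study Diary's fixed daily instruction cannot express the lowest pediatric dose level, whose whole reduction lies in two rest days

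*Combined protocol and SAP*

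**What the plan says.** All references are to the combined protocol and SAP.

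- **Dose table for children (Section 5.1.2).** A child on 15 mg is reduced to "15 mg/day daily for 5 days followed by 2 days rest", listed as a 29% decrease from the previous dose. A footnote to the table has antihypertensives held on the two rest days.
- **Pediatric blood pressure algorithm (Appendix J).** It describes the same level as a reduction "which results in taking cediranib on days 1-5 followed by 2 days rest", and repeats that antihypertensives are held on the rest days.
- **Limit on reductions (Section 5.1).** "A maximum of 2 dose reductions will be allowed before the patient is taken off treatment".
- **Starting doses (Appendix H).** Children start at 15, 20 or 30 mg according to body surface area: "Actual dose in mg (tablets sizes 15 and 20 mg) administered once daily".
- **Diary (Appendix C).** Staff fill in two blanks for tablet counts, but the frequency is preprinted. Page 2 reads "pills (15 mg) and ____ pills (20 mg) each day", and page 1 carries the same instruction, ending "pills (20 mg) each day". The two pages have one row for each of days 1 to 28. Neither has a field for a schedule or for rest days.
- **Use of the diary (Section 4.1).** "A new copy of the Study Diary will be given to patients whose dose is reduced due to adverse events". Parents receive the instructions too when the child cannot keep the diary alone.
- **Study Calendar, footnote a (Section 10).** "Dose as assigned administered orally, each day for 28 days (1 Cycle".

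**The concern.** Every other reduction in the protocol changes the tablet strength or the number of tablets, so the diary's two blanks can convey it. The step down from 15 mg is the exception. The tablet and the count stay the same, and the reduction consists only of days without drug. A form completed without error for this level (one 15 mg tablet, no 20 mg tablets) therefore reads exactly like the form for the regimen the child has just been taken off.

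The diary is the dosing instruction that the child or parent has at home. A child reaches this level because of a dose-modifying toxicity. Followed as printed, the form would cancel that step of the reduction. There is a linked conflict over blood pressure treatment: a family that took the study drug by the diary and the antihypertensives by the rest-day rule would give study drug on days when antihypertensives are held. Section 5.2.3 treats hypertension as one of the dose-limiting toxicities in children.

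**Working it through.** **Inputs.** Pediatric dose steps and stated percentages: Section 5.1.2. Maximum of two reductions: Section 5.1. Starting doses: Appendix H. Frequency and rows: Appendix C. Cycle length of 28 days: Section 4.1.

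**1. Reproduce the plan's own percentages.** Decrease = 1 − (new dose per week)/(previous dose per week).

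- 30 to 20 mg daily: 1 − 20/30 = 33.3% (table: 33).
- 20 to 15 mg daily: 1 − 15/20 = 25% (table: 25).
- 15 mg daily to 15 mg, five days on and two off: 1 − (15 × 5)/(15 × 7) = 1 − 75/105 = 28.6% (table: 29).

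All three agree. The third comes wholly from the two rest days.

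**2. The same step with the diary followed as printed.**

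- Per week: 15 × 7 = 105 mg by the diary, 15 × 5 = 75 mg by the table.
- Per 28 days: 15 × 28 = 420 mg (28 tablets) by the diary, 15 × 20 = 300 mg (20 tablets) by the table.
- Ratio: 420/300 = 1.40, so the diary gives 40% more than the table's level.
- Decrease at this step by the diary: 1 − 105/105 = 0%.

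**3. Which children are affected.** Two reductions are allowed. Total doses per 28 days at the start are 15 × 28 = 420, 20 × 28 = 560 and 30 × 28 = 840 mg.

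| Starting dose | Path | Total decrease by Section 5.1.2 | Total decrease if the diary is followed |
|---|---|---|---|
| 15 mg | 15 daily, then 15 with rest days | 1 − 300/420 = 28.6% | 1 − 420/420 = 0% |
| 20 mg | 20, then 15 daily, then 15 with rest days | 1 − 300/560 = 46.4% | 1 − 420/560 = 25% |
| 30 mg | 30, then 20, then 15 daily | 1 − 420/840 = 50% | 50% (rest-day level not reached) |

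Adult levels in Section 5.1.1 are 30, 20 and 15 mg, all daily, so the diary wording fits every one of them.

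**4. Days without antihypertensives.** Two rest days per week give 2 × 4 = 8 days in a 28-day cycle. Those are the days on which study drug could be taken while antihypertensives are held.

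**5. Is there another diary?** The table of contents lists one Study Diary, at page 67, with Appendix D starting at page 69. The two diary pages shown account for that space.

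**The case against.** The best reply is that the diary is a fill-in form and is not used alone. Section 4.1 has patients instructed in its use, involves parents where needed, and issues a fresh copy when the dose is reduced for an adverse event. Staff could strike out the daily wording and mark the rest days by hand. That is a fair point about likelihood. It does not remove the contradiction: nothing on the form prompts the correction, and what is printed describes the unreduced regimen.

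Footnote a of the calendar is weaker evidence than Appendix C. It opens by referring to the assigned dose and can be read as describing the default cycle. It is worth aligning, but the point does not depend on it.

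A reader might also infer more than the documents support:

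- *That every child at this level would get no reduction at all.* This is true only for a child who started at 15 mg. A child who started at 20 mg keeps the first 25% step.
- *That a child who takes the rest days fails the 90% cycle-completion rule, because 20 of 28 rows is 71%.* Section 4.1 counts prescribed doses. At this level 20 are prescribed, so 20/20 = 100%, and the rule needs no change.
- *That the record would show a reduction that did not take place.* The diary logs tablets by day, the bottle comes back with the form, and the office enters the cycle's tablet total. Daily dosing would show as 28 tablets where the table implies 20. The error would be visible, though only afterwards.

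Practical reach is limited. Section 2.4 reports a pediatric cohort of 7, accrual closed, and two pediatric patients still on drug. Their dose levels are not given. On the other side, Section 4.1 allows 4 cycles of drug to be dispensed at once after 36 cycles and 6 after 60, so the form may guide dosing at home for a long stretch.

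**Conclusion.** The point holds as an internal contradiction between the patient-facing form and the pediatric dose rules. At one step, from 15 mg daily to the rest-day level, following the diary as printed gives 105 instead of 75 mg per week and turns a 29% decrease into 0%. Two of the three pediatric starting doses can lead there: 15 mg at the first reduction and 20 mg at the second. Counting starting doses says nothing about how many children would reach the level.

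The conclusion rests on three assumptions: the form is handed over without a hand correction and is followed literally; the child's dose has not been changed for growth, which Section 5.1.2 permits; and, for the blood pressure conflict, the family applies the rest-day rule to antihypertensives while taking study drug daily. The documents do not show that any of this has happened to a patient, and they show no effect on the response endpoint, the sample size or the analysis. This is a safety-related correction to a form, worth making because it is cheap and specific.

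**What to change.** Reconcile Appendix C with Section 5.1.2 and Appendix J, so that the diary states the assigned schedule, including any rest days, in place of a preprinted daily frequency. A blank for the schedule next to the tablet counts, and a way to mark rest days among the 28 rows, would be enough. Align the wording of calendar footnote a in Section 10 at the same time, and check that the antihypertensive instruction on rest days matches whatever schedule the form then states. Which schedule applies is a clinical decision for the investigators, and no view is taken here.

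The cost is an edit to a two-page form and one footnote. It needs no extra visits, procedures or patients. The study team can tell from its own records whether either pediatric patient still on treatment is at this level.
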